SAMPLE SIZE	N=150 The main objective of the RE-CONNECT study is to demonstrate the efficacy of FeetMe home-based rehabilitation program compared to conventional physiotherapy at Week 12 in PD patients. The primary endpoint is the change from baseline to Week 12 in gait velocity (cm/s) assessed during the 6 Minutes Walk-Test (6MWT). The sample size computation is based on the study of Chris J Hass et al. (Hass et, al, 2014.) aiming to determine the Minimal Clinically Important Difference (MCID) for the gait velocity in patients with idiopathic Parkinson's disease. In this study including 324 patients, MCID for gait velocity was classified as small, moderate and large with values of 6 cm/s, of 14 cm/s and 22 cm/s respectively (using a distribution-based analysis and the categorization defined by Cohen (Cohen et al, 1988)). We aim to show that the Feetme rehabilitation procedure will allow to improve the change in gait speed at least in a moderate range in
	Improve the change in gait speed at least in a moderate range in comparison with that in standard rehabilitation group and we set the difference to be detected at 14cm/s. In the Chris J Hass et al, the standard deviation of gait velocity was estimated at 27 cm/s. To detect a difference of 14cm/s between the two groups for the change in velocity with a standard deviation of 27 cm/s for the change from baseline to Week 12 in gait speed (assuming a conservative correlation coefficient of 0.5 between the measures at baseline and at week 12), 60 patients per group are needed (two-sided Student's test, type I error of 0.05 and a power of 80%). To take into account a 20% rate of drop out for the measurement of the gait velocity at week 12 (15% of lost to follow up and 5% of deaths or injuries), we plan to recruit 75 patients per group (a total of 150 patients).

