STATISTICAL METHODS	The primary outcome (the change in the gait velocity between baseline and week 12, assessed during the 6 Minutes Walk-Test) will be estimated and compared between Feetme rehabilitation and conventional physiotherapy groups using the constrained longitudinal data analysis (cLDA) model proposed by Liang and Zeger, including centre as random effect and adjusted for the covariable "already in rehabilitation" considered as stratification factor in the randomisation. The between- group mean differences in 12-week change in gait velocity will be estimated by the time-by-arm interaction as treatment effect size. The assumptions of the cLDA model will be checked. We will use the analysis of cDLA model residuals by examining graphically the normality of residuals (histogram and Quantile-quantile plot) and by using the Shapiro Wilk test. In case of strong departure from the normality assumptions (even after applying a logarithmic transformation), nonparametric analysis will be used as recommended by Vickers et al.; absolute changes between baseline and 12-week will be calculated and compared between the 2 treatments groups using non-parametric analysis of covariance adjusted for baseline values. The effect size will be assessed by Hedges's g (standardized differences) computed on rank transformed data with its

	95% confidence interval (using the method based on noncentral Student distribution which is a corrected version of Cohen's d taking into account the sample size).				
BENEFIT/RISK CONSIDERATIONS	A risk analysis was carried out in accordance with ISO 14971 to identify the potential risks associated with the FeetMe Rehabilitation device. The residual risks are all at an acceptable level.				

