6 INVESTIGATIONAL PLAN

6.1 Study design and rationale

This is a multicentre, controlled, randomised in two parallel groups, open label study. The study will enroll 150 patients over approximately 18 months and 6 investigational sites.

Having multiple centres enrolling patients will not only maximise the capacity of recruitment but will allow for the evaluation of differences represented by geographical imbalances in the physiotherapy practices across France.

Patients who are found eligible and consent to participate will be randomised either on the conventional physiotherapy or on the FeetMe arm in a 1:1 ratio. Due to the set-up of the FeetMe program (i.e.: personal follow-up of the patients by an APA and the difference in the device needs between the two groups) and the obvious difference in the treatments, a blinded design is not possible. Nevertheless, the objective nature of the primary and main secondary endpoints measured by digital technology and the patient reported nature of most of the remaining outcome measures minimise any potential biassing effect originating from the open label design. Additionally, the final analysis will be performed by a independent blinded statistician.

The equal allocation of patients is maintained during the Primary Intervention Period (from the Baseline Visit till Visit 3) up to the primary endpoint evaluation at Week 12. It is in line with the duration of the FeetMe rehabilitation program. The program is built based on several regulatory recommendation including the HAS and the WHO and expert opinions suggesting that rehabilitation trainings typically show benefit after ten weeks. Additionally, most of the published data supports this duration together with the list of interventions analysed in the European Physiotherapy Guideline for Parkinson's Disease (Keus et al, 2014) where the median duration of the programs is eight weeks. The timing of the primary endpoint at Week 12 is adopted to this standard duration of an intensive rehabilitation therapy off approximately 3 months.

After the Primary Intervention Period patients will be offered to chose how to proceed i.e.: to continue on their original allocation, to switch arms or to stop treatment. In any case the patients will remain in the study until the week 26 EOS visit. The number of patients on the arms at this point will not be controlled and the data gathered will be exploratory in nature. This design is expected to:

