7.2.1.2 Randomisation

Eligible patients will be randomised using an Interactive Voice/Web Response System (IXRS) randomised either on the conventional physiotherapy or on the FeetMe arm in a 1:1 ratio. Randomisation will be stratified by the covariable "already in a rehabilitation program" and by study site. We will use a dynamic randomisation procedure by minimization using the Pocock and Simon method. Randomization will result in the assignement of the unique Patient ID, which will be used on all study-related documents pertaining to the patient. Any identification numbers that are assigned will not be reused even if the patient does not continue in the study.

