7.4 Primary Intervention Period

Following the Baseline Visit, all patients will begin their 12-week physiotherapy (or no-physiotherapy) regimen according to their randomisation.

During this period:

- All patients will participate in the Remote Gait Monitoring 1 and Visits 1-3 (Sections 7.3.1, 7.3.2, 7.3.3).
- Patients on the Conventional Physiotherapy arm, if they have access to it will start or continue their conventional physiotherapy and will keep track of it using the Conventional Physiotherapy Tracking Sheet (Appendix F). Patients who did not have access to CPt at the time of inclusion but manage to arrange one during the Primary Intervention Period will restart their PIP.
- On the other arm patients will start the FeetMe rehabilitation program (Section 4.4, Appendix A and B).
- In addition, all patients will keep a falls diary (Appendix G).

7.4.1 Remote Gait Monitoring 1

At the end of the Baseline Visit, all patients will take the FeetMe Insoles, mobile devices and chargers with them to their homes. A Patient User Guide will be provided.

- All patients will use the insoles remotely while performing their day-to-day activities (including physiotherapy) for two weeks. Data will be recorded in standalone mode (without a phone).
- Patients will download the data from the insoles at the end of each day.

7.4.2 Visits 1 and 2

Four and eight weeks after Baseline Visit, two remote visits (Visit 1 and 2) will take place. Patients will be asked to fill in the following questionnaires:

- PDSS-2
- Pain VAS
- Parkinson Disease Questionnaire, Short Form (PDQ-8).

7.4.3 Visit 3

Twelve weeks after Baseline Visit, that is, at the end of the 12-week Primary Intervention Period, all patients will participate in an in-clinic visit (Visit 3), where they will perform the same series of assessments as in the Baseline Visit. Patients will need to bring their FeetMe devices, their diaries, trackers and filled-in questionnaires to the visit.

The following assessments will be performed at Visit 3:

- Gait Assessments, which must be performed in the ON-phase:
 - 6 Minutes Walk Tests (6MWT)
 - Mini-BESTest.

During the 6MWT and the Mini-BESTest patients must wear the insoles. Specific instructions set out in the Site User Manual must be followed when setting up and executing the assessments.

- Disease specific rating scales:
 - MDS-UPDRS
- Other Assessments:
 - FOG-Q
 - PDSS2
 - Pain VAS
 - PDQ39

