9.5.1 Analysis for the primary endpoint

The primary outcome (the change in the gait velocity between baseline and week 12, assessed during the 6 Minutes Walk-Test) will be estimated and compared between Feetme rehabilitation and conventional physiotherapy groups using the constrained longitudinal data analysis (cLDA) model proposed by Liang and Zeger including centre as random effect and adjusted for the covariable "already in a rehabilitation program" considered as stratification factor in the randomisation. We chose to use cLDA model in view of its potential advantages compared to the conventional ANCOVA model. First, the cLDA model provides more flexibility in handling missing data by including all observed data, which, in general, results in more power when testing treatment differences compared with the longitudinal ANCOVA model. Second, compared with the ANCOVA model, the cLDA model provides more appropriate confidence interval estimates, especially in the context of randomised clinical trials where proper randomisation ensures baseline balance. In the cLDA model, both the baseline and postbaseline values are modelled as dependent variables using a linear mixed model (using an unstructured covariance pattern model), and the true baseline means are constrained to be the same for the 2 treatment groups. The between-group mean differences in 12-week change in gait velocity will be estimated by the time-by-arm interaction as treatment effect size. The assumptions of the cLDA model will be checked. We will use the analysis of cDLA model residuals by examining graphically the normality of residuals (histogram and Quantile-quantile plot) and by using the Shapiro Wilk test. In case of strong departure from the normality assumptions (even after applying a logarithmic transformation), nonparametric analysis will be used as recommended by Vickers et al. (reference: 1) Andrew J Vickers. Parametric versus non-parametric statistics in the analysis of randomised trials with non-normally distributed data. BMC Medical Research Methodology 2005, 5:35 2) Conover WJ, Iman RL: Analysis of covariance using the rank transformation. Biometrics 1982, 38:715-724.); absolute changes between baseline and 12-week will be calculated and compared between the 2 treatments groups using nonparametric analysis of covariance adjusted for baseline values. The effect size will be assessed by Hedges's g (standardized differences) computed on rank transformed data with its 95% confidence interval (using the method based on noncentral Student distribution which is a corrected version of Cohen's d taking into account the sample size). A sensitivity analysis will be performed excluding from the FAS population patients who have a change in levodopa medication during the first 3 months. For this sensitivity analysis, we will use the same methodology as that described for the primary analysis.

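### As written, the primary cLDA adjusts the two minimisation factors on the level of gait velocity but not on its 12-week change, a modest loss of precision if they affect change moderately or more

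*Protocol*

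**What the plan says.** The Synopsis (Statistical Methods) and Section 9.5.1 describe the same primary model. It is a constrained longitudinal model with unstructured covariance, in which baseline and Week 12 gait velocity are both dependent variables and the baseline mean is common to the arms. The factors enter as "including centre as random effect and adjusted for the covariable" for already being in rehabilitation. The effect of interest is fixed as follows: "The between-group mean differences in 12-week change in gait velocity will be estimated by the time-by-arm interaction as treatment effect size". No other term by time is named.

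These two factors also drive allocation. Section 7.2.1.2 stratifies by prior rehabilitation and study site and states: "We will use a dynamic randomisation procedure by minimization using the Pocock and Simon method".

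Two other places bear on whether the factors could affect change. In Section 7.4, control patients "if they have access to it will start or continue their conventional physiotherapy". In Section 6.1, having several centres "will allow for the evaluation of differences represented by geographical imbalances in the physiotherapy practices across France".

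Sections 9.2.4 and 9.5.2 reuse the primary method for the key secondary endpoint and the other continuous secondary endpoints. Section 9 leaves full analysis details to the SAP.

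**The concern.** In a model with both visits as outcomes, a covariable main effect and a random centre intercept add the same amount to baseline and Week 12. They explain why some patients walk faster than others, but not why some change more than others. The endpoint is the change.

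There are reasons to think that change could differ by factor. Controls already in rehabilitation carry on, while others start or have none. FeetMe patients already in rehabilitation suspend it (inclusion criterion 15). Sites are expected to differ in local physiotherapy.

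Minimisation balances the arms on both factors, so any common effect on change largely cancels from the arm difference. A model without by-time terms still counts that effect as residual noise. The standard error then overstates the real uncertainty, and precision that the allocation scheme has secured is not used.

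The protocol treats the factors differently elsewhere. In Section 9.5.3 the exploratory Week 12 to Week 24 comparison adjusts the change itself for the Week 12 value, the stratification covariable and centre.

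**Working it through.** **The plan's own figure.** Inputs from the Synopsis and Section 9.4: "we set the difference to be detected at 14cm/s"; the calculation is done "with a standard deviation of 27 cm/s for the change from baseline to Week 12 in gait speed"; correlation 0.5; two-sided 0.05; 80% power.
- SD of change = 27 × √(2 × (1 − 0.5)) = 27.
- Normal approximation: 2 × (1.960 + 0.842)² × 27² / 14² = 58.4, so 59 per group. The exact t calculation gives 60 (power 80.4%).
- 60 / 0.80 = 75 per group. The stated figures reproduce.
- SE assumed by that t-test: 27 × √(2/60) = 4.93 cm/s.

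**What a level-only adjustment leaves behind.** Assume half the patients are in each rehabilitation stratum, a between-stratum difference d in 12-week change, a between-site SD s in change, and complete data. Each visit has variance 27² = 729, and the covariance is 0.5 × 729 = 364.5. With equal variances, one main effect serving both visits settles halfway between its baseline value and its Week 12 value. Half of the shift is left over at each visit, with opposite signs. That adds q = (0.25d² + s²)/4 to each variance and takes q off the covariance:
- V = 729 + q and C = 364.5 − q
- Week 12 variance given baseline = V − C²/V (with q = 0: 729 − 182.25 = 546.75)
- SE of the arm difference = √(2 × that variance / 60)

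| d / s (cm/s, assumed) | q | Variance given baseline | SE | Ratio to q = 0 |
|---|---|---|---|---|
| 0 / 0 | 0 | 546.75 | 4.27 | 1.00 |
| 6 / 0 | 2.25 | 551.8 | 4.29 | 1.005 |
| 10 / 5 | 12.5 | 574.4 | 4.38 | 1.025 |
| 14 / 5 | 18.5 | 587.3 | 4.42 | 1.036 |
| 22 / 5 | 36.5 | 625.0 | 4.56 | 1.069 |

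**Simulation with dropout.** Settings: 150 patients, 20% missing at Week 12, six sites, minimisation with biased coin 0.8, centre coded as fixed, 600 runs per cell. The SE ratio of the as-written model to the model with factor-by-time terms was 1.00, 1.01, 1.03, 1.04 and 1.08 for the five rows above. The ratios run slightly higher than the formula because missing Week 12 values pull the fitted main effect towards baseline, which leaves more of the shift at Week 12. Against a completer ANCOVA with the same covariables, the as-written SE ratio was 0.99, 1.00, 1.02, 1.03 and 1.07.

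**Simulation with a random centre intercept, as the plan words it** (REML, 200 runs per cell, by-time model with fixed centres). SE ratios were 0.992 with no effect on change, 0.999 at d = 5, 1.007 at 10, 1.021 at 14, 1.029 at 10/5 and 1.089 at 14/10. Mean estimates ran from 13.9 to 14.5 for a true 14. The empirical SDs carry about 5% simulation error, and one cell (0/5) went the other way (4.49 against a model SE of 4.31). The SE ratios are therefore the figures to rely on.

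**Error rate and power.** At 22/5 the null rejection rate was about 2 to 3% as written, against 4.3% with by-time terms; with 600 runs the simulation error is a little under 1 point. Power for a true 14 cm/s in that scenario, with dropout, was 84% against 88%. With 60 completers per arm, SEs of 4.29, 4.41 and 4.55 give 90%, 88% and 86% power at 14 cm/s (t, 118 df).

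**The case against.** The strongest reply is that the protocol never says the adjustment is on level only. It names no factor-by-time term, but it excludes none either. A random centre effect could be read to include a centre-by-time component, and Section 9 leaves full details to the SAP, which is not shown. This stands: level-only is the literal reading of the terms listed, not an explicit statement. It does not remove the point, because the protocol spells out the model closely enough to single out one time interaction, and that interaction is arm.

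The effect sizes are also assumed. The 6, 14 and 22 cm/s in the Synopsis are categories of clinically important difference in gait velocity, not differences in change between strata. A 22 cm/s stratum difference would exceed the 14 cm/s treatment effect sought. This stands too, and the 8% figure should be read as an extreme case.

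Further, part of what the protocol describes is specific to an arm: FeetMe patients are followed remotely, so local practice acts mainly on controls. By-time terms common to both arms absorb only the average of such effects. That is a fair limit on the gain.

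A reader might infer that the interval is too wide whenever the factors affect change at all. The calculations do not support this: at 5 to 6 cm/s the loss is 1% or less, and with no effect the simpler model is marginally better (0.992).

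**Conclusion.** The point holds as one of precision. On the literal reading, the primary cLDA does not adjust the 12-week change for the two factors used in minimisation. If those factors have a moderate or larger effect on change, the model-based standard error is modestly too large: about 3 to 4% for 10 to 14 cm/s between strata with a site SD of 5 cm/s, and about 8% for 22 cm/s with that site SD. A 6 cm/s stratum shift alone costs about 1% or less. These sizes rest on an even split of prior rehabilitation, SD 27 cm/s, correlation 0.5, and effects on change that the documents do not give.

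A reader might go further and conclude that the primary test is invalid or the trial underpowered. Neither follows. The estimate showed no material bias, and the error goes in the conservative direction. Even the 4.56 cm/s SE in the largest tabulated case is below the 4.93 cm/s on which the trial was sized, so the stated 80% power at 14 cm/s is still met. Loss for the other endpoints that reuse the model was not quantified. This is a cheap improvement, not a correction of an error in a stated figure.

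**What to change.** In the Synopsis and Section 9.5.1, state that prior rehabilitation by time (fixed) and centre by time (random or fixed, six sites) enter the cLDA. Keep the common-baseline constraint across arms and the time-by-arm term as the treatment effect. Apply the same model to the key secondary and the other continuous secondary endpoints. If the SAP already contains these terms, the protocol need only say so.

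The cost is one sentence and a few degrees of freedom, with no new data. If neither factor affects change, the SE is essentially unchanged: the ratio was 1.00 in one simulation and 0.992 in the other, so at most about 1% is lost.

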4 BACKGROUND INFORMATION

4.1 Disease to be Assessed

4.1.1 Parkinson's Disease

Parkinson's Disease (PD) is the second most common neurodegenerative disorder after Alzheimer's disease and is characterised by a variety of motor and non-motor symptoms, including bradykinesia, rigidity, gait disorders, tremor and falls. PD is pathologically characterised by the presence of Lewy bodies, composed of aggregated and phosphorylated alpha-synuclein in the subcortical regions of the brain (Spillantini et al., 1997). Nevertheless, the underlying causes of neuronal death and alpha-synuclein deposits are still unknown and subject to intense study (Poewe et al., 2017). PD has an incidence of 5-35 cases per 100,000 individuals, with an overall estimated global prevalence of 0.3%, increasing sharply up to 3% when considering people over 80 years of age (Poewe et al., 2017). PD has an adult onset and it is rarely diagnosed before the sixth decade of life; its incidence in the population however increases dramatically starting from that time point (Van Den Eeden et al., 2003).

Idiopathic PD is characterised by a continuous progression of clinical symptoms and can be preceded by a prodromal phase lasting years or even decades, defined by a specific set of non-motor symptoms such as Rapid Eve Movement (REM) sleep behaviour disorder, depression, constipation, and anxiety. At their onset, motor symptoms are usually unilateral, an asymmetry usually persists through the course of the disease. Bradykinesia, rigidity, and tremor are the typical motor abnormalities of early-stage PD, leading the patient to seek medical attention and guiding the first diagnosis. As the disease progresses, more debilitating symptoms emerge, as motor fluctuations (on/off phases) and dyskinesias manifest (Poewe et al., 2017). Slow walking is a common manifestation of PD that negatively affects patients' performance in daily living activities (Mehrholz et al., 2016; Muslimović et al., 2008). Among the most burdensome characteristics of late-stage PD are instability of posture and gait abnormalities, oftentimes causing falls that can be quite harmful, frequently leading to hospitalisation and reduction in life expectancy ((Verghese et al., 2009, Fasano et al., 2017). Some studies reported that approximately 35% to 90% of PD patients fall at least once a year, with an average rate of 60.5% (Fasano et al., 2017; Pickering et al., 2007; Wood et al., 2002). In another work, it was estimated that roughly 39% of patients sustain multiple falls and fall-related injuries over one year (Allen et al., 2013). Given the high rate of falls during walking in people with PD and the significant burden they impose on quality of life as well as on the health care system, identifying individuals at higher risk and developing rehabilitation programs to reduce such risk is crucial. Motor symptoms are also supplemented by a set of non-motor manifestations which can greatly affect the quality of life of the patients, such as pain, cognitive impairment, apathy and autonomic dysfunction (Chaudhuri and Schapira, 2009).

Motor symptoms of PD develop quite rapidly if untreated. However, the introduction of Levodopa has greatly prolonged the progression time and it could take up to 15 years until the patient is in need of extensive assistance from their caregiver (Poewe, 2006). The mortality ratio in PD patients is between 1.5 and 2.5 times higher than the normal population. The average survival from symptoms onset is 10 years; however, these values are highly dependent on the age at onset and on the individual course of the disease.

